## 6.2 FIDELITY

### 6.2.1 INTERVENTIONIST TRAINING AND TRACKING

We will adhere to NIH guidelines on treatment fidelity. Failure of treatment fidelity is unlikely given that our program is video-based and delivered via text messages. Although we have not had technical problems in our prior studies, it is possible that they could occur in the future. We will bring a spare set of VR glasses and earbuds to the dental appointment to minimize this. In order to identify problems at the earliest point, we will continuously monitor outgoing and incoming texts from participants through a desktop dashboard that has this functionality. We will also document all technical problems on an eCRF. We have also created protocols to ensure that the active ingredients of the intervention are fully operationalized, ensured that the intervention components and measures are reflective of underlying theory, used feedback from preparatory research to refine adherence to the theoretical model and improve acceptability, feasibility, and potential effectiveness of the intervention; developed a plan to

record protocol deviations across both conditions; established a plan for implementation setbacks; assessed whether patients received smoking advice or intervention from providers, and ensured that written materials have appropriate health literacy.

Research staff will be trained in all aspects of study implementation which includes recruitment and enrollment (accessing electronic dental records, screening of potential study subjects using eCRF in REDCap, informed consent, text-message program opt-in procedures, and baseline questionnaire), intervention delivery (setting up materials and instrumentation, implementation of intervention or control video during teeth cleaning), and follow-up activities (sending questionnaires, tracking subject status, and retention). During the preparatory research phase, we have successfully piloted all relevant study procedures and developed a manual of procedures which will be adapted for this study. To ensure the highest standard of training and fidelity in the training of all study personnel, we will use the manual of procedures, conduct role plays, simulate clinic visit procedures, and conduct mock intervention delivery. A training checklist will be developed by the PI and Co-I and used during training sessions. All study personnel will be required to satisfy the checklist criteria before initiating any study procedure. Research staff training and quality control procedures regarding the collection and processing of saliva samples are described in detail in a separate protocol (Saliva sampling procedures – including remote sampling – 06.18.20).

### 6.3 MEASURES TO MINIMIZE BIAS: RANDOMIZATION AND BLINDING

We will conduct a stratified block randomization procedure with small, random size blocks. Participants will be randomized to one of two groups, Intervention or Control, after completing the baseline assessment, the in-clinic eligibility screener (to ensure that their smoking status has not changed since the screener), and receipt of brochure. Randomization will be stratified by motivation to quit (ready to quit smoking in 30 days vs. not ready to quit within 30 days). Only the PI, the project director, the statistician, and the clinic RAs (RAs who are setting up the video for each patient) will be unmasked to treatment condition. These RAs will not be involved in the collection of any outcome data. Because both the Intervention and Control groups will be watching a video, all dental providers will be able to be masked to participant's treatment condition. The RA who performs follow-ups and collection of saliva cotinine will be masked to treatment condition.

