attempts and increase their motivation to quit; 2) To test the efficacy of the Intervention vs. Controls on biochemically verified smoking abstinence. Hypothesis 3 states: Participants in the Intervention will achieve higher rates of point-prevalence abstinence at follow-up; 3) To assess the mechanisms through which intervention effects occur (mediators such as self-efficacy, motivation, and outcome expectations) and to identify subpopulations for whom intervention effects differ (moderators such as gender and motivation to quit). Hypothesis 4 states: The Intervention will directly affect the putative mediators of intervention effect, which will in turn affect EBT engagement (contact) and utilization. The role of moderators will be exploratory.

Participants will be randomized (1:1) at the dental clinic, after receiving the study brochure and before watching the videos during their teeth cleaning. Randomization will be implemented by employing a stratified block procedure with small, random size blocks and will be stratified by motivation to quit (ready to quit smoking in 30 days vs. not ready to quit within 30 days). To avoid randomization errors, randomization will be configured within REDCap, the secure web application used to build and manage the questionnaires and study forms which is programmed and managed by the BU Biostatistics and Epidemiology Data Analytics Center (BEDAC). A biostatistician will build the randomization program. The study RA will trigger randomization by pressing the feature on the REDCap eCRF form using an iPad. All dental providers will be masked to treatment condition because both the Intervention group and the Control group will be watching a video through the VR headset. Only the PI, project director, statistician, and study RA who is in the clinic will be unmasked to treatment condition.

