### 6.1.2 ADMINISTRATION AND/OR DOSING

The study has several phases. At Time 1 after receiving the study brochure, participants will be randomized to watch either the Intervention or Control videos using the VR headset and earbuds during part of their dental cleaning at the GSDM patient treatment center or at the TU comprehensive care (or periodontal) clinic. Before administration of the video intervention, a study RA will perform instrumentation (set up correct video according to randomization parameters and motivation to quit status, ensuring patient comfort and equipment functionality) while the patient is in the dental chair before the beginning of dental cleaning. Following the dental care provider signal to initiate dental cleaning procedure, the RA will start the video and patients will watch the video through the VR headset. All videos are approximately 10 minutes in length. Once the video has concluded, the RA will

remove the VR headset from the participant and exit the room. The Principal Investigator, project director, statistician, and the clinic study RA will be unmasked to treatment condition. Since all participants will be watching a video, dental providers remain masked to treatment condition.

With 24-hours of their dental appointment, the Intervention group will begin receiving the 4-week text message curriculum to motivate and facilitate utilization of EBT resources for smoking cessation. The text message program includes two tracks, one for those who are motivated to quit and one for those who are not motivated to quit. The administration and dosing of the program curriculum will be as follows:

- 'Introduction' text messages in Week 1.
- Approximately 1-2 intervention text messages per day ('core messages'). These intervention texts target social cognitive mediators, motivate contact with EBTs, and also dispel myths about smoking cessation medications and other EBTs.
- Weekly 'Assessment' text messages each week (to measure social cognitive mediators).
- Weekly 'Transition' text messages beginning on day 7 (to facilitate participants' transition to one or more EBT resources).
- 'Check-in' text messages in week 2 – 4, scheduled to be delivered approximately 5 days after the 'Transition' text message (to check in on participants' transition to EBTs).

The control group will receive mediators 'Assessment-only' text messages.

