### 9.4 STATISTICAL ANALYSES

#### 9.4.1 GENERAL APPROACH

For descriptive statistics, categorical data will be presented through percentages and continuous variables will be presented through means and standard deviations. For statistical tests, a two-tailed  $p$ -value less than 0.05 or a 95% confidence interval not including the null value will be used for statistical significance.

EBT utilization will be analyzed by computing a utilization index score (UIS). The UIS will be created by first computing a proportion of utilization score for each of the EBTs for each participant. For example, a participant who completed 4 of 5 quitline calls has a proportion score of 80. For NRT, the recommended length of treatment is 8 weeks and the proportion completed by each participant will be computed. For the NCI smoke-free text message program, the recommended length of participation is 56 days, and we will compute the proportion of days completed, as well as the proportion of text messages responded to (of those that required a response). For clinic-based programs, the proportion will be calculated as the number of sessions attended divided by maximum number of sessions offered at the corresponding clinic. Because participants may use one or more EBT programs, the overall “utilization index score” will be the sum of the above individual proportion scores of each EBT for each person. These individual scores will be summed to obtain the UIS (continuous variable). The distribution of our UIS will be examined for approximate normality, and transformations to improve normality or categorization of the index score will be considered if appropriate. For primary analyses, we will control for age, gender, and race/ethnicity, along with variables identified through preliminary analyses as significantly differing between study groups.

This study will be registered with Clinical Trials.gov prior to the start of participant enrollment.

A formal Statistical Analysis Plan (SAP) will be completed prior to the completion of the study and the unblinding of the study data.

---

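### The SAP is to be fixed before unblinding, but the statistician, PI and project director are already listed as unmasked, so that trigger does not protect the choices still open on the primary endpoints

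*Combined protocol and SAP*

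**What the plan says.** **Timing of the SAP.** Section 9.4.1: "A formal Statistical Analysis Plan (SAP) will be completed prior to the completion of the study and the unblinding of the study data". It gives no date and no data-lock milestone, and does not define unblinding. Section 4.4 places the end of the study at the final assessment, 6 months after the end-of-treatment assessment.

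**Who is unmasked.** Section 4.1: "Only the PI, project director, statistician, and study RA who is in the clinic will be unmasked to treatment condition". Section 6.1.2, describing the clinic visit: "The Principal Investigator, project director, statistician, and the clinic study RA will be unmasked to treatment condition". Section 6.3 lists the same roles: "Only the PI, the project director, the statistician, and the clinic RAs (RAs who are setting up the video for each patient) will be unmasked". None of the three says that unmasking is delayed.

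**Stated safeguards.** Section 6.3 masks the dental providers. Of the clinic RAs it says: "These RAs will not be involved in the collection of any outcome data". It adds: "The RA who performs follow-ups and collection of saliva cotinine will be masked to treatment condition".

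**What is still open.** Section 3 lists the UIS as a primary endpoint, and section 9.4.2 analyses it by multiple linear regression. Section 9.4.1 adds that "transformations to improve normality or categorization of the index score will be considered if appropriate", with no rule, named transformation or cut-point. For SmokefreeTXT it names two proportions (days completed and messages answered) without saying how they enter the sum. Both models in section 9.4.2 adjust for age, gender and race/ethnicity, plus any variable found to differ significantly between arms.

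**The concern.** Fixing a SAP before unblinding protects a trial because those who settle the analysis cannot know which option favours an arm. That needs a moment before which they lack the arm codes. Here three senior roles, including the statistician, are described as having them, with no such moment stated.

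At stake is the credibility of the UIS result. With most scores expected at zero, the normality check in section 9.4.1 is likely to fail, so the choice between raw, transformed and categorized scores will probably have to be made. If it were made by someone who could compare the forms by arm, even without intent, the nominal 5% level would not hold for that endpoint, and a reader could not rule this out. Section 9.2 makes no multiplicity adjustment that would absorb the excess.

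**Working it through.** The plan gives no figure on this point. The check is a comparison of sections, then an illustration of size.

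**1. Does the trigger mark a point in time?** Section 9.4.1 sets two limits: unblinding of the data and completion of the study. For the roles listed in 4.1, 6.1.2 and 6.3, unmasking is stated without a start date, and 6.1.2 states it when describing the randomization visit. The first limit therefore fixes no clear date for them. By section 4.4 the second is the last participant's last assessment, so a SAP signed just before it would come after nearly all follow-up. The current version is dated 12 September 2024, month 50 of the 60 months (08/01/2020 to 07/31/2025), and still refers to the SAP in the future tense.

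**2. Do the other safeguards cover analysis choices?** Those in 6.3 protect care delivery and outcome collection. No section provides a masked analyst, withheld or dummy arm codes, or a bar on linking outcomes to allocation before the SAP is signed.

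**3. Which open choices can depend on arm?**
- UIS form and the SmokefreeTXT combining rule: can be settled on pooled data, but nothing requires it.
- Covariates: the between-arm screen cannot be run without arm grouping. Section 9.4.5 says only that differing variables will be considered as potential confounders, whereas 9.4.2 says they will be controlled for, so discretion remains.

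**4. How much could the UIS choice matter?** Inputs from section 9.2: 455 × 0.80 = 364 analysed, or 182 per arm at 1:1; any use 22.7% (Control) and 37.6% (Intervention), so 77.3% and 62.4% of scores would be zero.

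Assumptions: no true effect; users contact 1 + Binomial(3, 0.2) EBTs; each proportion is 100 × Beta(0.8, 1.0), on the 0-100 scale of the section 9.4.1 example. Five forms: t-test on the raw score, on log(1 + x) and on the square root; and two splits, at 50 and at 100, each tested by z = [(x − y)/n] / √[2P(1 − P)/n], where x and y are the numbers at or above the cut in each arm, n = 182 and P is the pooled proportion. The tests are unadjusted. Rejection rates at two-sided 0.05 over 20,000 null trials per row:

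| Users in both arms | Any one fixed form | Best of 3 (raw, log, root) | Best of 5 (adding two cuts) |
|---|---|---|---|
| 22.7% | 4.8-5.1% | 7.0% | 11.3% |
| 30% | 4.9-5.2% | 6.9% | 11.5% |
| 37.6% | 5.0-5.3% | 7.2% | 11.9% |

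Simulation error is small: √(0.115 × 0.885 / 20,000) = 0.0023. Independent tests would give 1 − 0.95³ = 14.3% and 1 − 0.95⁵ = 22.6%; the simulated rates are lower because the forms are correlated.

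With uniform proportions instead, raw and log alone gave 6.0%; raw, log and root gave 5.7-6.8%. Raw, log and splits at >0, >0.5 and >1 (scores as fractions) gave 11.4-12.6% across runs, and 10.4% without the >0 split, which essentially repeats the any-use endpoint.

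**The case against.** The strongest reply is that knowing individual allocations is not the same as seeing results by arm. Unblinding of the study data can mean release of a dataset with arm attached, and on that reading the sentence in 9.4.1 has content. The statistician listed as unmasked may be only the biostatistician who builds the randomization program (section 4.1), with someone else doing the analysis. Section 10.1.5, on key roles, was not available to this review and may say so. No interim analysis is planned (9.4.6).

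The open choices are also limited. Section 9.4.2 names linear regression with a difference in means, and the normality check needs no arm comparison. The any-EBT endpoint, on which the sample size rests, has a fixed logistic model apart from its covariates. The primary missing-data approach is stated (participants evaluated at 6 months); multiple imputation and weighting are secondary.

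Much of this stands. A reader might infer that the unmasked staff will write the SAP while viewing outcomes by arm from the start. The documents do not support that: they name no SAP author in the text available, do not date the unmasking, and give no one early by-arm access to outcomes. Nor do they show most primary data already in REDCap: quitline records come from its operator and SmokefreeTXT data from the program, with no transfer date given.

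What does not stand is that the ambiguity is harmless. If unblinding means linkage of outcomes to arm, the plan should say so and name who holds the codes.

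**Conclusion.** The point holds as a gap in a claimed protection. For the roles listed as unmasked, the unblinding trigger fixes no clear date, and the remaining limit is too late to help. Bias is possible and unguarded; none is shown.

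The size is conditional. If one UIS form is fixed in advance, type I error stays at about 5%. If the form were picked on by-arm results, it would be about 6-7% with transformations only and about 11-12% with cut-points also tried. These figures rest on an assumed score shape, an assumed menu and a deliberate search for the smallest p-value. The documents mention categorization but no cut-points, so 11-12% should not be read as the trial's actual error rate. The covariate screen is the one choice that explicitly depends on arm; its effect was not quantified.

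**What to change.** In sections 9.4.1 and 6.3:

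1. Replace the unblinding trigger with a SAP signed and dated before any outcome data are linked to allocation. Section 4.1 puts both randomization and questionnaires in REDCap, so define linkage as any export, report or analysis file containing both.
2. Have data management (BEDAC) hold the allocation table and release analysis files without arm codes until sign-off. State who holds the codes and who writes the SAP.
3. Fix the UIS formula now, including how the two SmokefreeTXT proportions combine. Fix its form now too, or choose it by a stated rule on pooled data without arm.
4. Replace the between-arm covariate screen with a prespecified list that includes the randomization stratum (readiness to quit within 30 days).
5. Record in the SAP whether anyone had seen outcomes by arm before signing. Taking the statistician off the unmasked list would not undo knowledge already held; a dated lock and this statement are more useful.

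The cost is earlier SAP work, REDCap user rights and wording. Sample size and power figures do not change. The downside is that no one has by-arm outcome data before sign-off, which no planned analysis needs (9.4.6).

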### 6.4 STUDY INTERVENTION/EXPERIMENTAL MANIPULATION ADHERENCE

Text message program. The Agile Health Platform keeps track of all text messages sent and received, including both unprompted responses and expected responses from participants. This includes responses to assessment questions, and responses to the interactive intervention features of the text message programs. In order to identify technical problems or problems of non-compliance at the earliest point, we will continuously monitor outgoing and incoming texts from participants through a desktop dashboard that has this functionality. The study team will also receive weekly reports from Agile Health on adherence indicator (e.g., percent of assessment texts responded to; percent of intervention texts responded to; non-responders) consistent with procedures tested in the preparatory research phase. We also meet with Agile Health once per week to monitor participant adherence. Any technical or adherence issue will be documented on an eCRF.

Intervention. Adherence to the VR video intervention component which takes place during dental cleaning will be monitored by the study RA who will be in the treatment room when the patient is in the dental chair watching the allocated video through the VR headset. The RA will bring a spare VR headset and earbuds in case of technical issues. Any technical or adherence issue will be documented on an eCRF.

## 6.5 CONCOMITANT THERAPY

N/A

### 6.5.1 RESCUE THERAPY

N/A

## 7 STUDY INTERVENTION/EXPERIMENTAL MANIPULATION DISCONTINUATION AND PARTICIPANT DISCONTINUATION/WITHDRAWAL

### 7.1 DISCONTINUATION OF STUDY INTERVENTION/EXPERIMENTAL MANIPULATION

If a participant is unable or unwilling to wear the VR headset, the participant will be deemed as “ineligible after randomization.”

When a participant discontinues from the text message program but not from the study, remaining study procedures will be completed as indicated by the study protocol.

Reasons the subject may be discontinued from the study intervention include

- Participant does not have time to participate in text messaging.

The data to be collected at the time of study intervention discontinuation will include the following:

- The reason(s) for discontinuing the participant from the intervention, and methods for determining the need to discontinue. This will be recorded on an eCRF.
- If the participant is due to complete assessments within 2 weeks of being discontinued from the study intervention, those assessments will be administered at the time of discontinuation; if the next scheduled assessments are more than 2 weeks from the discontinuation date, the discontinued participant will wait for the next scheduled assessment. Thereafter, the participant will be included in all future scheduled assessments, even though not participating in the intervention.

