Participants will watch the videos through a VR headset during their teeth cleaning. The VR headset we used during the UG3 usability study (Viotek Spectre) was rated highly comfortable by participants. However, if a participant feels uncomfortable wearing the headset during the video, he or she may remove it. In this case, we will terminate participation and compensate the participant accordingly.

There are two potential risks of text messaging: accidents, thumb, and joint pain. Frequent texting may increase the risk of thumb and joint pain. The number of texts involved in this study is not likely to result in thumb and joint pain. To prevent text message-related injury, we will inform participants that text messages should not be attended to while driving or walking. In a previous pilot study that included a similar text message curriculum participants received for two months, there were no issues related to fatigue interacting with text messages, and the text message program was well received by participants.

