## 5.2 EXCLUSION CRITERIA

An individual who meets any of the following criteria will be excluded from participation in this study:

1. Participation in another treatment or intervention study for smoking cessation or research involving text messaging.
2. Current use of medications for smoking cessation or smoking reduction (nicotine replacement product, or non-nicotine medications) whether prescribed or not.
3. Failure to complete the pre-dental clinic appointment procedure before the start of the dental appointment (e.g., informed consent, opt-into the text message program and complete the baseline questionnaire).
4. Failure to show up to the scheduled dental appointment at the BU or TU clinic.
5. Previous participation in the UG3 Usability study or pre-award pilot study.

6. Inability to watch the video with the VR headset during the dental appointment.

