### 7.2 PARTICIPANT DISCONTINUATION/WITHDRAWAL FROM THE STUDY

Based on the NIH Behavioral and Social Intervention Clinical Trial Protocol Template v3.0 - 20180827

Participants are free to withdraw from participation in the study at any time upon request. An investigator may discontinue a participant from the study for the following reasons:

- Participant becomes dangerous to self or others.
- Lost-to-follow up; unable to contact subject (see Section 7.3, Lost to Follow-Up)
- Any event or medical condition or situation occurs such that continued collection of follow-up study data would not be in the best interest of the participant or might require an additional treatment that would confound the interpretation of the study
- The participant meets an exclusion criterion (either newly developed or not previously recognized) that precludes further study participation

The reason for participant discontinuation or withdrawal from the study will be recorded on the attrition Case Report Form (CRF). Subjects who sign the informed consent form and are randomized but do not receive the study intervention may be replaced. Subjects who sign the informed consent form, and are randomized and receive the study intervention, and subsequently withdraw, or are discontinued from the study, will not be replaced. If the subject becomes ineligible, then we will replace the subject but only if the study is within the specified recruitment period.

We will attempt to obtain a final questionnaire assessment and saliva sample (if necessary per protocol) from all subjects who withdraw from the study for any reason. We will make a minimum of 5 attempts to contact the subject in cases of withdrawal and those who relocate.

This study may be suspended or prematurely terminated if there is sufficient reasonable cause. Written notification, documenting the reason for study suspension or termination, will be provided by the suspending or terminating party to investigator and NIDCR. If the study is prematurely terminated or suspended, the principal investigator will promptly inform the IRB and will provide the reason(s) for the termination or suspension. Circumstances that may warrant termination include, but are not limited to:

- Determination of unexpected, significant, or unacceptable risk to subjects.
- Insufficient adherence to protocol requirements.
- Data that are not sufficiently complete and/or evaluable.
- Determination of futility.

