### 9.3 POPULATIONS FOR ANALYSES

We will conduct intention-to-treat (ITT) analyses where we include all patients based on their randomized groups, regardless of their subsequent withdrawal from treatment or deviation from the protocol. Primary analyses will be based on participants who are evaluated at 6-month follow-up. In the case of missing data, we will collect reasons for dropout to inform our assumption about missing mechanism. Secondary analyses using multiple imputation or inverse probability weighting to account for missing data will be explored. Sensitivity analyses will be performed to explore the effects of departures from assumptions made in these missing-data analyses.

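### Randomised participants who cannot or will not wear the headset are declared ineligible, dropped and replaceable, which contradicts the stated intention-to-treat analysis

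*Combined protocol and SAP*

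**What the plan says.** Allocation comes first. Sections 4.1 and 6.1.2 place randomisation after the brochure and before the video; the headset is then set up in the dental chair.

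Several rules remove people after that moment:

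- Section 7.1: "If a participant is unable or unwilling to wear the VR headset, the participant will be deemed as" ineligible after randomisation.
- Section 2.3.3, on a participant who takes the headset off because it is uncomfortable: "In this case, we will terminate participation and compensate the participant accordingly".
- Section 5.2, exclusion criterion 6: "Inability to watch the video with the VR headset during the dental appointment".
- Section 7.2: "Subjects who sign the informed consent form and are randomized but do not receive the study intervention may be replaced". The same paragraph says that people who received the intervention and were then discontinued are not replaced. It then says that a subject who becomes ineligible is replaced while recruitment is open.
- Section 9.2 takes 20% off the 455 randomised. That allowance covers losses to follow-up together with post-randomisation ineligibility, and the split is not given.

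Against these, Section 9.3, repeated in 9.4.2, promises an intention-to-treat analysis in which "we include all patients based on their randomized groups, regardless of their subsequent withdrawal from treatment or deviation from the protocol". The next sentence of both sections bases the primary analysis on those assessed at six months.

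**The concern.** These statements cannot all hold. A person who is randomised and then refuses or removes the headset has deviated from the protocol or stopped treatment. Section 9.3 keeps such a person in the comparison, while Sections 2.3.3, 7.1 and 9.2 put that person outside it. Nothing says how these people, or their replacements, enter the analysis.

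The issue is more than lost numbers. One arm watches a smoking-cessation video and the other a relaxation video. The research assistant who sets up the headset knows the allocation (Section 6.3). A smoker with little interest in quitting may be more likely to take off a headset that shows cessation content, and may also be less likely to use an EBT. If such people leave the Intervention denominator more often than the Control denominator, the remaining groups are no longer those that randomisation made comparable. Replacing them restores the headcount but not the comparability.

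**Working it through.** **1. The plan's own power figure.** Inputs from Section 9.2: any-EBT rates of 22.7% (Control) and 37.6% (Intervention), two-sided alpha 0.05, 455 randomised 1:1, 20% removed. (The synopsis and Section 4.1 carry other totals, which is a separate matter.)

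455 × 0.80 = 364, or n = 182 per arm. With p̄ = 0.3015,

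Power = Φ{[0.149 − 1.96·√(2p̄(1−p̄)/n)] / √([p1(1−p1) + p2(1−p2)]/n)} = Φ{(0.149 − 0.0943)/0.0475} = Φ(1.15) = 0.875.

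The plan states 0.87, so the figure reproduces. With all 455 in the denominator the same formula gives 0.936. The stated power is therefore calculated with post-randomisation ineligibles outside the analysis.

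**2. Timing of the rules.** The order is brochure, randomisation, headset set-up, video. Exclusion criterion 6 and the rules in Sections 2.3.3 and 7.1 all turn on events at or after headset set-up. None can be applied before allocation.

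**3. Possible bias under no true effect.** The documents give neither the number of headset exclusions nor the EBT rate among those excluded, so these are assumptions. Let the true rate be p = 0.227 in both arms, let a share x of an arm be excluded, and let those excluded have EBT rate q. The rate among those left is (p − xq)/(1 − x).

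For type I error I start from 182 per arm, so n = 182(1 − x), and take z = difference/SE with unpooled SE. The two-sided error is 1 − Φ(1.96 − z) + Φ(−1.96 − z).

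| Excluded, Intervention v Control | q | Rates left, Intervention v Control | Spurious difference (points) | Type I error |
|---|---|---|---|---|
| 5% v 2% | 10% | 23.4% v 23.0% | 0.4 | 0.051 |
| 5% v 2% | 0% | 23.9% v 23.2% | 0.7 | 0.053 |
| 10% v 2% | 10% | 24.1% v 23.0% | 1.2 | 0.057 |
| 10% v 2% | 0% | 25.2% v 23.2% | 2.1 | 0.073 |
| 15% v 5% | 10% | 24.9% v 23.4% | 1.6 | 0.063 |
| 15% v 5% | 0% | 26.7% v 23.9% | 2.8 | 0.090 |

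Worked line for the last row: 0.227/0.85 − 0.227/0.95 = 0.2671 − 0.2389 = 0.0281. SE = √(0.2671×0.7329/154.7 + 0.2389×0.7611/172.9) = 0.0481. z = 0.584. Error = 0.0844 + 0.0055 = 0.090.

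If x and q are the same in both arms the formula gives the same rate in each, so there is no bias and only a loss of numbers.

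**4. Cost of analysing everyone.** Keep n = 227.5 per arm and count a share x of each arm as non-users, so that both rates are multiplied by (1 − x):

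| x | Power | Odds ratio |
|---|---|---|
| 2% | 0.93 | 2.04 |
| 5% | 0.92 | 2.02 |
| 10% | 0.90 | 1.99 |

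If the whole 20% were counted as non-users, power would be 0.85.

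**The case against.** The best defence is that few people will be affected, and not differentially. Section 2.3.3 reports that usability participants found the headset comfortable, and it ties removal to discomfort rather than to content. Fitting and comfort checks come before the video starts (Section 6.1.2), so refusal at that stage cannot be a reaction to what is shown. This stands in part: arm-dependent removal is a possibility, not something the documents show. But Section 7.1 also covers unwillingness, Section 2.3.3 covers removal while the video plays, and the person fitting the headset is unmasked.

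A second defence is that follow-up is protected elsewhere. Section 7.1 keeps those who stop only the text messages, and Section 7.2 attempts a final questionnaire from those who withdraw. Neither provision says that a person terminated or declared ineligible over the headset is assessed at six months, which is what entry to the primary analysis requires.

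A reader might also infer something stronger: that people who start cessation medication after randomisation would be removed, although medication use is a primary-outcome event. Section 7.2 lists as a ground for discontinuation: "The participant meets an exclusion criterion (either newly developed or not previously recognized) that precludes further study participation". Exclusion criterion 2 is: "Current use of medications for smoking cessation or smoking reduction (nicotine replacement product, or non-nicotine medications) whether prescribed or not". The documents do not support that inference. The rule is discretionary and limited to criteria that rule out continuing. The intervention promotes medication, and Sections 8.1 and 9.4.2 count it over seven months. Section 7.2 says that people treated and then discontinued are not replaced. Moreover, removing the same share s of EBT users from both arms multiplies both odds by (1 − s), so the odds ratio stays at 2.05 and only precision is lost. What remains is a gap in wording: criterion 2 is not expressly limited to the period before randomisation.

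**Conclusion.** The contradiction is in the text and needs no assumption. Sections 2.3.3, 5.2, 7.1, 7.2 and 9.2 remove randomised participants for events that can only occur after allocation, while Sections 9.3 and 9.4.2 promise to analyse everyone as randomised. The replacement sentences in Section 7.2 also conflict with each other for a treated participant who is later found ineligible.

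The size of any bias is unknown. Under the assumed exclusions it runs from negligible (0.4 points, type I error 0.051) to moderate (2.8 points, 0.090). It favours the Intervention only if removal is commoner in that arm and those removed are less likely to use EBTs. The documents do not show that the trial is biased. They show that the primary denominator is undefined, and that people dropped without follow-up would leave no means of checking.

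**What to change.** Reconcile Sections 2.3.3, 5.2, 7.1, 7.2, 9.2, 9.3 and 9.4.2 as follows:

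- Eligibility closes at randomisation. Not wearing, or stopping, the headset afterwards is recorded as non-adherence.
- Every randomised participant who has not withdrawn consent stays in follow-up and in matching to quitline and SmokefreeTXT records.
- All randomised participants enter the primary analysis, including those who never started or did not finish the video, under a missing-outcome rule stated in advance. This has to replace the six-month-evaluated restriction in Sections 9.3 and 9.4.2; otherwise the same people still drop out.
- Extra recruits are additions and displace no one already randomised. The conflicting replacement sentences in Section 7.2 are resolved accordingly.
- Post-randomisation ineligibility comes out of the 20% allowance in Section 9.2.
- Any analysis limited to those who watched the video is supportive only.
- As a wording note, exclusion criterion 2 is stated to apply before randomisation.

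Participants remain free to take the headset off. The cost is wording, some further follow-up surveys, and possibly slight dilution (odds ratio 2.05 to about 1.99 if 10% per arm are counted as non-users). This version is dated September 2024 and the study is due to end in July 2025, so some people already terminated may be past survey follow-up. Their number should be reported by arm and their outcomes handled under the missing-outcome rule, using programme records where consent allows.
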